Hypothesis	
This is a pilot study designed to assess the relationship between iFR pullback and the distribution of coronary atheroma/stenoses as assessed by Quantitative Coronary Angiography (QCA) post angiographically successful PCI. The hypotheses of this study are:
 
 1. iFR is impaired in a substantial proportion of patients following operator-assessed angiographically successful PCI 2. Post-PCI iFR detects residual significant CAD that is not detected on QCA (defined by $\geq 50\%$ stenosis) 3. Post PCI iFR is predictive of future adverse cardiovascular events
Objectives	
 1. Determine the range of post-PCI iFR and the rate of significant residual ischemia defined as iFR < 0.90 following operator-assessed angiographically successful PCI 2. Determine the proportion of cases in which the iFR would become non-significant if a focal stenosis demonstrated by iFR pullback were treated with PCI. This will be the number or

	
proportion used in the sample size calculation for the planned randomized trial.
 
 3. Determine the relationship between post-PCI iFR pullback and QCA with respect to residual stenosis by QCA, residual stenoses and device success (i.e. optimal stent implantation). The goal is to correlate abnormal iFR measurements to their anatomic reason (i.e. device related complications, angiographically undetected residual lesions, or diffuse atherosclerotic disease). 4. Determine the relationship between post-PCI iFR and clinical outcomes, such as recurrent angina and MACE. 5. Establish the relationship between post-PCI iFR and objective assessment of quality of life.

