
Study Design and Methods
	
DEFINE-PCI is a multi-center, prospective study in up to 25 centers in USA and internationally. Consented subjects with CAD who undergo physiologic lesion assessment with iFR<0.90 in at least 1 coronary artery are eligible for participation. After successful PCI to all culprit lesions based on angiographic assessment of the treating physician, a blinded post-PCI iFR and iFR pullback will be performed. The proportion of patients with impaired post-PCI iFR will be assessed, and the number of patients in whom ischemia could theoretically be normalized with further PCI determined. Additionally, the association between the post-PCI iFR results and cardiovascular events and clinical symptoms will be assessed. Follow-up will be at 1, 6 and 12 months, including administration of quality of life questionnaires.

Number of subjects
	
An exact one sample binominal proportion test will be used for analysis of the primary endpoint. Assuming a 10% rate of residual $\geq 50\%$ stenosis based on QCA versus a conservative 15% rate of iFR<0.90 with a two-sided type I error of 0.05, approximately 500 patients will be required to achieve 90% power.

Primary Endpoint
	
Rate of residual ischemia defined as iFR <0.90 after operator-assessed angiographically successful PCI (residual diameter stenosis <50% in any treated lesion in the target vessel)

Secondary Endpoint
	
Secondary clinical endpoints (assessed in relation to post PCI iFR ([as dichotomous and continuous variable]):
 
 1. Composite of cardiac death, target vessel myocardial infarction, ischemia-driven target vessel revascularization or recurrent ischemia at one year (definition below) 2. Target vessel failure defined as cardiac death, target vessel myocardial infarction, ischemia-driven target vessel revascularization 3. Quality of life (assessed by the Seattle Angina Questionnaire) at baseline, 30-days, 6 months and 1year 4. All-cause and cardiac mortality at one year 5. Target vessel Myocardial infarction at one year 6. Ischemia-driven target vessel revascularization at one year

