- Composite of cardiac death, target vessel myocardial infarction, ischemia-driven target vessel revascularization or recurrent ischemia at one year (definition below)
- Target vessel failure defined as cardiac death, target vessel myocardial infarction, ischemia-driven target vessel revascularization

-
- Quality of life (assessed by the Seattle Angina Questionnaire) at baseline, 30-days, 6 months and 1year
 - All-cause and cardiac mortality at one year
 - Target vessel Myocardial infarction at one year
 - Ischemia-driven target vessel revascularization at one year
 - Recurrent ischemia at one-year

Secondary physiology endpoints:

[figure not shown]
- Correlation between iFR <0.90 and coronary stenosis $\geq 50\%$ assessed by visual interpretation
- Proportion of cases in which the iFR would become non-significant if a focal stenosis demonstrated by iFR pullback were treated with PCI
- Differentiation of the cause for impaired iFR (categorized as stent related, distant focal stenosis, or diffuse atherosclerosis)
- Predictors of delta iFR before and after PCI

Secondary clinical endpoints will be evaluated using iFR in a dichotomous fashion with a cut-point of iFR<0.90 as well as iFR as a continuous variable.

STUDY DESIGN

Overview

This is a prospective, single-arm, multi-center, pilot study to assess the relationship between iFR pullback and the distribution of coronary atheroma/stenoses as assessed by Quantitative Coronary Angiography (QCA) post angiographically successful PCI.

Methods

Consented subjects with CAD who undergo physiologic lesion assessment with $iFR < 0.90$ in at least 1 coronary artery are eligible for participation. After successful PCI to all culprit lesions based on (visual) angiographic assessment of the treating physician, a blinded post-PCI iFR pullback will be performed. The proportion of patients with impaired post-PCI iFR will be assessed, and the number of patients in whom ischemia could theoretically be normalized with further PCI determined. Additionally, the association between the post-PCI iFR results and cardiovascular events and clinical symptoms will be assessed. Follow-up will be at 1, 6 and 12 months, including administration of quality of life questionnaires.

Treatment Arms

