11. Participation in any investigational study that has not yet reached its primary endpoint.
12. Known severe renal insufficiency (eGFR < 30 ml/min/1.72 m²).
13. TIMI flow < 3 at baseline of study vessel
14. Intra-coronary thrombus on baseline angiography

Study Procedures

Baseline (up to 30 days prior to index procedure)

Prior to any study-specific procedures, the subject's written informed consent will be obtained. Basic demographic data will be collected, a targeted history and physical examination focused on the study limb. Female subjects of childbearing potential must have a negative pregnancy test within 7 days of the index procedure in order to participate. If the subject meets all Inclusion Criteria and none of the Exclusion Criteria, and provides written informed consent, he/she may be enrolled in the study.

- Informed Consent
- Medical History
- Current antianginal medications
- CBC and platelet count (if performed as SOC)
- Troponin or CK-MB (If performed as SOC)
- Complete metabolic panel (if performed as SOC)
- EKG
- Echocardiogram (if performed)
- Ischemia assessment (if performed) – TTE/nuclear/MRI/CCTA
- Seattle Angina Questionnaire

Pre PCI Procedure

[figure not shown]
Subjects are taken to the procedure room and appropriate anesthesia is administered per institutional standards. Assessments:

- Angiography
- Baseline iFR of each vessel intended for PCI
- Drift Check after each vessel assessment
- UADE assessment
- IVUS/OCT (if performed as SOC)
- iFR Pullback should not be performed during pre pci assessment. This is a major protocol deviation.

Angiographic Assessment

- Intracoronary Nitrates
- Orthogonal views of any potential target vessel in which 1 or more stenosis is at least 40% by visual assessment.

PRE-PCI PHYSIOLOGICAL ASSESSMENT

*When pulling the wire back to check for drift, it is a MAJOR protocol deviation to perform this under the iFR pullback mode.

[figure not shown]
PCI Procedure

- Create a second case in the Volcano system for the blinded data
- If Verrata wire is used for the PCI, it must be renormalized prior re-crossing the lesion
- Any coronary guidewire can be used
- Perform PCI in accordance with the local PCI guideline and protocols
- IVUS/OCT (if performed as SOC)
- Visual assessment of final angiographic results documented

Post PCI Procedure (Blinded Data)

- If re-inserting Verrata wire, it must be renormalized.
- Perform Post PCI iFR measurements of each vessel treated

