The primary endpoint, the proportion of patients with RI defined as iFR < 90, is computed using maximum likelihood analysis. We compute the maximum likelihood estimate as $p = N^{-1} \sum_{s=1}^N y_s$, and Clopper – Pearson 95% confidence intervals.

The null hypothesis states no difference in the proportion of RI from 10%, or more formally, $H_0: p - 0.10 = 0$. The alternative hypothesis concludes any difference in RI from 10%, or $H_a: p - 0.10 \neq 0$.

Sample size computation

We assume a 10% rate of RI in the study (?) population which is defined as a residual stenosis of $\geq 50\%$ on QCA.

With 500 enrolled patients, type I error held at 5%, and the ability to detect a proportion of 15% RI, this study is powered at 90%.

Secondary Endpoint analysis

Kaplan Meier's product limit estimate computed as $S(t) = \prod_{t_j < t} \left(1 - \frac{d_j}{n_j}\right)$, where we partition time into j intervals t_j based on events, will measure time to event endpoints (listed as secondary endpoints 1-5). We conclude a significant survival difference between any two groups with the logrank test, and hold the expected type I error to 5%. We correct the type I error of the 5 related survival hypothesis using Benjamini and Hochberg's False Discovery Rate.

This protocol models Quality of life (secondary endpoint 6) as a mixed linear model,

$Q_{ijt} \sim N(\beta_0 + F_j[\beta_1 + b_{1j}T_j] + \beta_2T_j, \Sigma)$, where β 's describe fixed effects, b 's describe random effects, Σ describes a compound symmetric covariance matrix, and N the multivariate Gaussian distribution. We parameterize the covariance matrix with Compound symmetry, as opposed to autoregressive, because within time points will dominate variability compared to across time points.

The Kappa statistic will measure agreement between iFR and QCA's ability to detect RI by computing $\kappa = \frac{(p_e - p_1)}{(1 - p_1)}$, or the difference between empirical agreement and chance agreement divided by chance disagreement.

We estimate the proportion of cases in which the iFR would become non-significant if a focal stenosis demonstrated by iFR pullback were treated with PCI (Secondary endpoint 8) by

$$p = \frac{\#(\text{Number of non - significant iFR pullbacks})}{\#(\text{Patients})}$$

And assess the significance using a Binomial test.

The cause for impaired iFR is summarized using proportions, and the χ^2 test assess the null hypothesis that each cause of impaired iFR occurs at the same rate.

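### The quality-of-life mixed model gives the pre-PCI SAQ score no stated role and, on the usual reading, no fixed iFR-by-time term, so a pre-existing gap may be read as an association with post-PCI iFR

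*Combined protocol and SAP*

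**What the plan says.** The objective in the Study Summary is to "Establish the relationship between post-PCI iFR and objective assessment of quality of life". The endpoint is listed there as item 3: "Quality of life (assessed by the Seattle Angina Questionnaire) at baseline, 30-days, 6 months and 1year". The first of these scores is taken at the visit headed "Baseline (up to 30 days prior to index procedure"), so it precedes both PCI and the post-PCI iFR reading. The Secondary Endpoints section adds that the clinical endpoints are to be "evaluated using iFR in a dichotomous fashion with a cut-point of iFR<0.90 as well as iFR as a continuous variable". The Treatment Arms section calls the study nonrandomized.

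For the analysis, the SAP (Secondary Endpoint analysis) states: "This protocol models Quality of life (secondary endpoint 6) as a mixed linear model". The printed mean is β0 + F[β1 + b1j·T] + β2·T, with compound-symmetric covariance. The β's are called fixed, and the SAP adds that "b 's describe random effects". The only F-by-T coefficient is therefore labelled random.

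The documents do not define F, T, the subscripts or the mean of b1j. They do not say which visits enter Q or which coefficient carries the test. Nothing makes the baseline SAQ a covariate or defines a change in SAQ. The endpoint number does not help either: in the numbered list of the Study Summary, item 6 reads "6. Ischemia-driven target vessel revascularization at one year".

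**The concern.** Patients with low and normal post-PCI iFR are observed groups and may differ in angina before PCI. Post-PCI iFR cannot have influenced a score taken before the procedure. An analysis that either averages that score into the iFR contrast or ignores it cannot separate two findings: that patients with low post-PCI iFR report worse angina afterwards, and that they were already worse beforehand.

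The risk runs both ways. A pre-existing gap can appear as an iFR association, and a real post-PCI difference can be diluted by a visit at which it could not yet exist. What is at stake is the interpretation of the quality-of-life objective.

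**Working it through.** The documents give no power or effect size for quality of life, so there is no plan figure to reproduce here. The only stated power, 90% for the primary endpoint, does reproduce: the exact binomial test with 500 patients, 10% versus 15%, rejecting at 65 or more or 36 or fewer, has power 90.8%.

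**Inputs from the documents.** N = 500 and "a conservative 15% rate of iFR<0.90" (Study Summary, Number of subjects) give 75 versus 425 patients. Visits are at 0, 1, 6 and 12 months.

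**Assumptions.** F is post-PCI iFR below 0.90. Data are complete, and SAQ is in SD units with equal variance at each visit. Visit correlation r is 0.3, 0.5 or 0.7. Tests are two-sided at 0.05 (the SAP states 5% for the primary and logrank tests but not for this model). b1j has mean zero and, at first, no variance.

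**Step 1: what β1 estimates.** Under compound symmetry with complete visits, β1 is the group difference in each patient's mean over the modelled visits. With four visits and gaps g0 to g3, β1 = (g0 + g1 + g2 + g3)/4.
- Stable gap g: β1 = g, returned in full.
- Difference d only after PCI: β1 = 3d/4 = 0.75d. With patient-level slope variance of 0.05 to 0.2 of the visit variance (per year squared), this becomes 0.741d down to 0.685d.
- Linear or categorical time gives the same answer.

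With follow-up visits only, β1 is the mean follow-up gap, with no allowance for a gap that was there before.

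**Step 2: standard errors.** Let k = 1/75 + 1/425 = 0.01569.

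| Analysis | SE formula | r = 0.3 / 0.5 / 0.7 |
|---|---|---|
| Printed, four visits | √[k(1+3r)/4] | 0.086 / 0.099 / 0.110 |
| Printed, follow-up only | √[k(1+2r)/3] | 0.091 / 0.102 / 0.112 |
| Follow-up adjusted for baseline | √[k((1+2r)/3 − r²)] | 0.083 / 0.081 / 0.070 |
| Change from baseline | √[k((1+2r)/3 + 1 − 2r)] | 0.121 / 0.102 / 0.079 |

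**Step 3: expected estimates under three patterns.** The fading pattern has gap g at baseline and r·g at each follow-up visit, so there is no association once baseline is known.

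| Analysis | Post-PCI-only d | Stable gap g | Fading gap g |
|---|---|---|---|
| Printed, four visits | 0.75d | g | g(1+3r)/4 |
| Printed, follow-up only | d | g | r·g |
| Adjusted for baseline | d | (1−r)g | 0 |
| Change from baseline | d | 0 | −(1−r)g |

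**Step 4: rejection probability.** This is Φ(z − 1.96) + Φ(−z − 1.96), where z = |estimate|/SE. Example: four visits, r = 0.5, d = 0.3 gives z = 0.225/0.099 = 2.27 and power 0.62.

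| Analysis (r = 0.3 / 0.5 / 0.7) | Power, d = 0.3 SD | Rejection, stable 0.2 SD gap | Rejection, fading 0.2 SD gap |
|---|---|---|---|
| Printed, four visits | 0.74 / 0.62 / 0.53 | 64 / 52 / 44% | 20 / 24 / 29% |
| Printed, follow-up only | 0.91 / 0.83 / 0.76 | 59 / 50 / 43% | 10 / 16 / 24% |
| Adjusted for baseline | 0.95 / 0.96 / 0.99 | 39 / 24 / 14% | 5% |
| Change from baseline | 0.70 / 0.83 / 0.97 | 5% | 21 / 16 / 12% |

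A simulation of 4,000 runs agrees for the power and stable-gap columns (for example 0.735 / 0.620 / 0.528 and 64.5 / 52.9 / 44.6% in the first row).

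**The case against.** **The equation is ambiguous.** Q carries subscripts i, j and t, but only j appears on the right-hand side. If j indexes the iFR group, b1j is a group-specific time slope, close to the interaction that seems to be missing. If b1j is a patient coefficient with a free mean, that mean is an iFR-by-time slope. This stands: a reader might infer that the plan definitely leaves out an iFR-by-time term, and the documents do not settle that.

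It does not rescue the plan as written. With a free mean and four visits, a post-PCI-only d gives a slope of about 0.63d per year and a stable gap gives 0, so the patterns are separated. Power at d = 0.3 SD is only 0.30, 0.39 and 0.59 for r = 0.3, 0.5 and 0.7, even with no slope variance. With follow-up visits only, both patterns give slope 0. On no reading is the baseline SAQ given a stated role.

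**The objective asks only for a relationship.** A difference in average score is a relationship, the study is called a pilot, and none of its three hypotheses concerns quality of life. This stands as a limit on weight. The plan should still say whether it means level or change.

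**A gap is hypothetical.** A reader might infer that the iFR groups do differ before PCI, or that the result will be spurious. The documents contain no such data.

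**Change from baseline is not a cure.** It is protected against a stable gap only. For a fading gap at r = 0.3 it rejects in 21%, against 20% (four visits) or 10% (follow-up only) as printed.

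**Conclusion.** The concern holds in a limited form. The missing role for the baseline SAQ is plain from the text. The missing fixed iFR-by-time term depends on reading b1j as a mean-zero random effect, and reading F as post-PCI iFR is an inference from the objective. On those readings, four modelled visits return a stable pre-PCI gap in full and dilute a post-PCI-only difference to about 0.75d; follow-up visits alone leave a pre-existing gap unadjusted.

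Adjusting follow-up scores for baseline has more power than either printed variant and a lower false-positive rate under both gap patterns, at every correlation tried. It still leaves about (1 − r) of a stable gap. The sizes are illustrative: they rest on planning numbers, complete data and assumed correlations. Whether the groups differ at baseline is unknown. The SAP should be changed, but the primary endpoint is not affected.

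**What to change.** Make the main quality-of-life analysis a mixed model of the 30-day, 6-month and 12-month SAQ scores. Include post-PCI iFR, visit as a category, fixed iFR-by-visit terms and baseline SAQ as a covariate. Name the iFR difference averaged over follow-up as the target. Run it with iFR dichotomous and continuous, as the Secondary Endpoints section already requires. Report change from baseline as a sensitivity analysis, noting that it assumes a pre-existing gap would have stayed constant.

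As clarification, define every symbol in the model and correct the endpoint number. State which rule under Handling Missing data covers the baseline SAQ: list-wise deletion applies if it counts as an endpoint, and the under-5% imputation rule if it counts as a covariate.

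The cost is SAP wording and a few more parameters. SAQ is already scheduled at all four visits, no patients are added, and the main analysis loses no power in the scenarios shown. The sensitivity analysis has less power at low correlation (0.70 at r = 0.3).

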	
7. Recurrent ischemia at one-year
 
Secondary physiology endpoints:
 
8. Correlation between iFR <0.90 and coronary stenosis $\geq 50\%$ assessed by visual interpretation
 
9. Proportion of cases in which the iFR would become non-significant if a focal stenosis demonstrated by iFR pullback were treated with PCI
 
10. Differentiation of the cause for impaired iFR (categorized as stent related, distant focal stenosis, or diffuse atherosclerosis)
 
11. Predictors of delta iFR before and after PCI

Inclusion Criteria	
1. Subject must be ≥ 18 years old
 
2. Subjects presenting with stable angina, silent ischemia or non-ST-elevation ACS (unstable angina or biomarker positive)
 
3. Single vessel CAD with at least 2 separate lesions (≥ 10 mm apart) of $\geq 40\%$ stenosis or a single long lesion of ≥ 20mm OR multi-vessel CAD, defined as at least 2 vessels with $\geq 40\%$ stenosis
 
4. Pre-PCI iFR performed in all vessels intended for PCI
 
5. Pre-PCI iFR of <0.90 of at least 1 stenosis
 
6. Subjects are able and willing to comply with scheduled visits and tests and to provide informed consent.

Exclusion Criteria	
1. Pregnant or planning to become pregnant for the duration of the study
 
2. Acute STEMI within the past 7 days
 
3. Cardiogenic shock (sustained (>10 min) systolic blood pressure < 90 mmHg in absence of inotropic support or the presence of an intra-aortic balloon pump).
 
4. Inotropic or temporary pacing requirement
 
5. Sustained ventricular arrhythmias
 
6. Prior CABG
 
7. Known ejection fraction $\leq 30\%$
 
8. Chronic Total Occlusion (CTO) of study vessel
 
9. Known moderate to severe mitral or aortic disease.
 
10. Any known medical comorbidity resulting in life expectancy < 12 months.
 
11. Participation in any investigational study that has not yet reached its primary endpoint.
 
12. Known severe renal insufficiency (eGFR <30 ml/min/1.72 m²).
 
13. TIMI flow <3 at baseline of study vessel
 
14. Intra-coronary thrombus on baseline angiography

Sample size considerations	N=500 patients
Definition of recurrent ischemia	Recurrent ischemia is defined as ischemia meeting any of the criteria below: ¹

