Although iFR is increasingly used for physiologic assessment of coronary lesions prior to PCI, data on post-PCI iFR values is limited, and it is unclear how often coronary physiology remains abnormal after PCI, and whether PCI performance could be improved by routine use of iFR pullback. This study is designed to assess the relationship between iFR pullback and the distribution of coronary stenoses as assessed by Quantitative Coronary Angiography (QCA) following angiographically successful PCI. The hypotheses of this study are:

- iFR is impaired in a substantial proportion of patients following operator-assessed angiographically successful PCI.
- Post-PCI iFR detects residual significant CAD that is absent on QCA (defined by $\geq 50\%$ stenosis)
 - This could be due to:-
 - The presence of stenosis which are not apparent on angiography
 - The presence of diffuse disease
 - Sub-optimal PCI result
- Post PCI iFR is predictive of future adverse cardiovascular events

STUDY OBJECTIVES

- Determine the range
- of post-PCI iFR and the rate of significant residual ischemia defined as iFR <0.90 following operator-assessed angiographically successful PCI
- Determine the proportion of cases in which the iFR would become non-significant if a focal stenosis demonstrated by iFR pullback were treated with PCI. This will be the used in the sample size calculation for a future randomized trial.
- Determine the relationship between post-PCI iFR pullback and QCA with respect to residual stenosis by QCA, residual stenoses and device success (i.e. optimal stent implantation). The goal is to correlate abnormal iFR measurements to their anatomic reason (i.e. device related complications, angiographically undetected residual lesions, or diffuse atherosclerotic disease).
- Determine the relationship between post-PCI iFR and clinical outcomes, such as recurrent angina and MACE.
- Establish the relationship between post-PCI iFR and objective assessment of quality of life.

STUDY Endpoints

Primary Endpoints

- Rate of residual ischemia defined as iFR <0.90 after operator-assessed angiographically successful PCI (residual diameter stenosis <50% in any treated lesion in the target vessel)

Secondary Endpoints

Secondary clinical endpoints (assessed in relation to post PCI iFR ([as dichotomous and continuous variable]) :

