- Perform Post PCI iFR Pullback measurements of each vessel treated
- Drift Check should occur after each vessel iFR pullback
- No additional IVUS/OCT imaging after final iFR measurements
- No additional treatment after final iFR measurements, unless urgent/emergent needs arise.

BLINDED POST PCI PHYSIOLOGICAL ASSESSMENT

Blinding Procedure

During the post-PCI iFR pullback, and the remainder of the study, these steps should be taken when possible to ensure Investigator and other Blinded research staff continue to be blinded to the results.

Index Procedure Post PCI iFR Pullback

- Monitors (with integrated systems) will be turned off in the catheter laboratory procedure room. With a mobile unit, the screen will be turned away from the Investigator. Investigator will perform blinded iFR pullback under fluoroscopy.
- A second case will be created in the Volcano system for the Blinded portion of the study. This case will not contain patient identifiers and it will not be archived to the hospital archiving system.
- The blinded data (case #2) will be closed out immediately after the PCI, so the operator does not have visibility of the blinded data.
- Un-blinded catheter laboratory staff and/or research staff will burn the blinded data to a DVD, and will then be deleted from the Volcano system once confirmation the data is on the disk. Blinded data will not be documented in catheter laboratory procedure notes or patients chart.
- For sites where the cases are automatically pushed to an archiving system (i.e. PACS, Heart lab), it will be necessary to ensure the post-PCI iFR pullback (blinded data) does not get archived with the patients procedural images and data.
- The catheter laboratory staff will be educated on the importance of the blinded data; to ensure they do not share the information with the Investigators or blinded research staff.

Immediately after the index procedure:

- The un-blinded research staff will secure the blinded data. There is no written blinded data- only the data on the disk. The data will be transferred electronically to the core lab and will then be secured in a sealed envelope in the subject binder in the research office. . Only to be opened by monitors for source document verification, then resealed.

Follow up Phone Calls/Visits

- A blinded research staff member will be assigned to perform the follow up phone calls/visits with the subject.

Post Procedure to Discharge

- CBC and platelet count (if performed as SOC)

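### The SAP formula for the proportion correctable by focal PCI counts vessel-level pullbacks over patients, so it is not a binomial proportion, and its binomial test has no null value

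*Combined protocol and SAP*

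**What the plan says.** The quantity is an objective and a secondary physiology endpoint. The Study Summary (Objectives) says: "Determine the proportion of cases in which the iFR would become non-significant if a focal stenosis demonstrated by iFR pullback were treated with PCI". The endpoint list repeats it as "Proportion of cases in which the iFR would become non-significant if a focal stenosis demonstrated by iFR pullback were treated with PCI". Study Objectives adds its purpose: "This will be the used in the sample size calculation for a future randomized trial". The design text, in the Study Summary and under Study Design (Methods), puts it in patients: "the number of patients in whom ischemia could theoretically be normalized with further PCI determined".

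The SAP (Secondary Endpoint analysis) restates the endpoint and then gives the estimator as a fraction. The numerator is the "Number of non - significant iFR pullbacks" and the denominator is patients. The next line reads "And assess the significance using a Binomial test", with no null value.

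Two other places bear on this:

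- Post PCI Procedure (Blinded Data): "Perform Post PCI iFR Pullback measurements of each vessel treated". Multi-vessel disease is one of the routes to eligibility.
- Primary Endpoint Analysis, which does state its null: "The null hypothesis states no difference in the proportion of RI from 10" (10%). That null concerns the rate of residual ischemia. The same section specifies Clopper-Pearson 95% intervals.

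**The concern.** Three things do not fit together.

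1. **Conditions.** The endpoint is hypothetical and applies to patients whose iFR is impaired after PCI. The numerator mentions neither the impairment nor the predicted value after focal treatment.
2. **Unit.** The numerator is a count of vessels and the denominator a count of patients. A patient can contribute 0, 1, 2 or more to the numerator, so the sum is not a binomial count. No rule says how a patient with several impaired treated vessels is classified for this endpoint.
3. **Test.** A binomial p-value needs a null proportion, and none is given.

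At stake is an estimate that the protocol commits to the sample size of the next trial. An inflated or ambiguous value would carry over into that calculation.

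**Working it through.** **The plan's own figure.** No figure is stated for this endpoint. The only power figure is for the primary test: N=500, 10% against 15%, two-sided 5%, 90% power. The exact binomial test with 2.5% in each tail rejects at 36 or fewer or at 65 or more, with actual type I error 0.037 and power 90.8%. The stated 90% is reproduced, and nothing below touches it.

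**Inputs for the unit problem**

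- Impaired after PCI: 15%, the plan's own alternative; 0.15 x 500 = 75 patients.
- c, the share of impaired vessels that are correctable: 0.5 (assumed).
- m, the share of impaired patients with two impaired treated vessels, the rest having one: 10%, 20% or 30% (assumed).

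**Formulas**, each over all patients, with the numerator read through the lead-in:

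- Vessel count, as the formula has it: 0.15 x c x (1 + m)
- Patient level, both vessels of a patient always agreeing: 0.15 x c
- Patient level, independent vessels, all must normalise: 0.15 x [(1 - m)c + mc²]
- Patient level, independent vessels, any one suffices: 0.15 x [(1 - m)c + m(1 - (1 - c)²)]

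| m | Vessel count | Vessels agree | Independent, any | Independent, all |
|---|---|---|---|---|
| 10% | 8.25% | 7.50% | 7.88% | 7.13% |
| 20% | 9.00% | 7.50% | 8.25% | 6.75% |
| 30% | 9.75% | 7.50% | 8.63% | 6.38% |

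**Ratio of vessel count to patient-level value** (the 15% cancels):

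- Vessels agree: 1 + m = 1.10, 1.20, 1.30.
- Independent, any: (1 + m)/(1 + 0.5m) = 1.05, 1.09, 1.13.
- Independent, all: (1 + m)/(1 - 0.5m) = 1.16, 1.33, 1.53.

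At m = 0 every ratio is 1, so there is no error when each patient has one treated vessel.

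**The test.** Suppose 38 correctable patients of 500 (half of 75 is 37.5, rounded up). The exact two-sided p-value is 0.013 against a null of 5% and 0.074 against 10%. Both nulls are illustrations, since the plan offers none for this endpoint. The Clopper-Pearson 95% interval needs no null: 38/500 = 7.6% (5.4% to 10.3%).

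**The case against.** The strongest reply is that the lead-in and the fraction form one sentence. The lead-in defines the quantity and the fraction abbreviates it. This largely stands. A reader might infer that the formula would return about 85%, because 425 of 500 patients would have a normal iFR if 15% are impaired. That requires detaching the fraction from its lead-in and taking a non-significant pullback to mean a measured iFR of at least 0.90, a definition not found in the text. The objectives, design and endpoint sections all describe the hypothetical quantity, so the documents do not support 85% as a realistic result. The wording of the numerator is loose, and that is all this part shows.

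A reader might also infer that the all-patient denominator is wrong. The formula says patients, that choice is acceptable, and the primary endpoint rate converts it to a share of impaired patients.

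On size, the documents give neither the share of patients with two impaired vessels nor the correctable share, and the upper figure of 53% depends on independence between vessels of one patient. All the values in the table (6.4% to 9.8%) lie within the illustrative interval of 5.4% to 10.3%. This also stands, but the excess is systematic and would not shrink with more patients.

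Finally, no decision hangs on the p-value, since the later trial would use the estimate. That lowers the importance of the missing null, but a test that cannot be run should still not stay in the SAP.

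**Conclusion.** The point holds on the unit, the missing conditions and the missing null. Even on its most favourable reading, the estimator puts vessels over patients where the design text counts patients, and so it is not the binomial proportion that its test assumes.

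Under the assumed 10-30% with two impaired vessels and 50% correctable, the overstatement is 10-30% if vessels agree (0.75 to 2.25 percentage points). Under independence it is 5-13% with an any-vessel rule (0.4 to 1.1 points) or 16-53% with an all-vessel rule (1.1 to 3.4 points). It is zero if every patient has one treated vessel. These are illustrations, not predictions.

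It should be fixed because the estimate is designated for sizing a randomized trial. It does not affect the primary endpoint, its power or N=500.

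**What to change.** In Secondary Endpoint analysis:

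- **Numerator:** the number of patients with post-PCI iFR <0.90 in at least one treated vessel whose predicted iFR, after removal of the focal pullback gradient, is >=0.90 in every impaired treated vessel. The every-vessel rule fits the design text, which speaks of patients whose ischemia could be normalised.
- **Denominator:** keep patients, specified as those with an analysable post-PCI iFR and pullback. This agrees with the list-wise rule under Handling Missing data.
- **Inference:** replace the binomial test with the Clopper-Pearson 95% interval already used for the primary endpoint.

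The cost is a few lines of SAP text, best settled before data lock, and a written description of how the core lab identifies a focal gradient and derives the predicted iFR. The core lab already receives the tracings. No new data and no change to N are needed.
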